9.3. Variables

9.3.1. Exposure of Interest

Administration of ABRYSVO post-approval (ie, 31 May 2023) will be identified based on the following (see Annex 3 Table A-1 for additional details):

- Current Procedural Terminology (CPT) code 90678, OR
- 10 and 11-digit National Drug Codes (NDCs) 0069-0207-01, 0069-0250-01, 0069-0344-01, 0069-0344-05, 0069-0344-10, 0069-0651-01, 0069-1265-10, 0069-1265-20, 0069-2465-19, 0069-2465-01, 0069-2465-10; OR
- Immunization records that contain data on vaccine code descriptor, vaccine manufacturer (ie, Pfizer), lot number, injection site, and date(s) of immunization.

Relevant codes will be reviewed and amended if new codes are added.

9.3.2. Outcomes

The study's primary outcome, new onset atrial fibrillation, will be identified by a diagnosis code for atrial fibrillation in any setting during the 0-3 day risk interval (or 0-1 day or 0-30 day risk interval for secondary analysis), or corresponding control interval, followed by a confirmatory diagnosis within 30 days after the initial diagnosis. To be considered an incident case, no diagnosis for atrial fibrillation or other supraventricular arrhythmia should be observed in the 2 years prior to the index date (ie, "clean window," the occurrence-free

baseline period used to define incident outcomes during which individuals enter the study cohort only if the safety event did not occur during this period).^{8,9}

The secondary outcome of the study will be new onset supraventricular arrhythmia, including atrial fibrillation, and will be identified in the same manner as the primary outcome (ie, a diagnosis code for the event in any setting during the risk interval, or control interval, followed by a confirmatory diagnosis within 30 days after the initial diagnosis, and no diagnosis code for atrial fibrillation or other supraventricular arrhythmia in the 2-year clean window).

The study outcomes and operational definitions of the outcome variables based on International Classification of Diseases, Tenth Revision, Clinical Modification (ICD-10-CM) diagnosis codes are outlined in Table 1. ICD-10-CM diagnosis codes occurring in any position (ie, primary or secondary) in OP (including emergency department [ED]) and/or IP settings will be used to identify safety events.

Table 1. Safety events, including outcome algorithms and risk and control intervals

Safety Event	Operational Definition Defined by the presence of any of the following ICD- 10-CM codes (inclusive):	Setting (IP, OP)	Clean Window	Risk Interval (Days)	Post- Vaccination Control Interval for SCRI Design (Days)
Atrial fibrillation (primary outcome) ⁵⁰	 I48.0, Paroxysmal atrial fibrillation I48.19, Other persistent atrial fibrillation I48.20, Chronic atrial fibrillation, unspecified I48.91, Unspecified atrial fibrillation 	IP or OP	2 years	Primary: 0-3 Secondary : 0-1 and 0-30	Primary: 4-10 Secondary: 2-8 and 31- 61
Supraventricular arrhythmia, including atrial fibrillation (secondary outcome) ⁵⁰	Paroxysmal tachycardia I47.0, Re-entry ventricular arrhythmia I47.10, Supraventricular tachycardia, unspecified I47.11, Inappropriate sinus tachycardia I47.19, Other supraventricular tachycardia I47.9, Paroxysmal tachycardia, unspecified Atrial fibrillation:	IP or OP	2 years	Primary: 0-3 Secondary : 0-1 and 0-30	Primary: 4-10 Secondary: 2-8 and 31- 61

Table 1. Safety events, including outcome algorithms and risk and control intervals

Safety Event	Operational Definition Defined by the presence of any of the following ICD- 10-CM codes (inclusive):	Setting (IP, OP)	Clean Window	Risk Interval (Days)	Post- Vaccination Control Interval for SCRI Design (Days)
	See "Atrial fibrillation (primary outcome)" above				
	 Atrial flutter: 148.3, Atrial flutter 148.4, Atypical atrial flutter 148.92, Unspecified atrial flutter 				
	Other cardiac arrhythmia: • I49.1, Atrial premature depolarization • I49.5, Sick sinus syndrome • I49.8, Other specified cardiac arrhythmias including Brugada syndrome, coronary sinus rhythm disorder, ectopic rhythm disorder, nodal rhythm disorder				

Abbreviations: ICD-10-CM, International Classification of Diseases, Tenth Revision, Clinical Modification; IP, inpatient; OP, outpatient.

The risk intervals were selected based on published literature and biological plausibility. ¹⁰⁻¹⁷ A safety event will be counted if it can be assigned to 1) the risk interval following ABRYSVO, 2) the post-vaccination control interval (SCRI design), or 3) risk interval for the contemporary vaccinated or unvaccinated controls. The risk intervals for outcome evaluation for contemporary vaccinated or unvaccinated controls will be the same as for individuals who received ABRYSVO.

Events outside these intervals will not be counted. Only the individual's first instance of a safety event following the 2-year clean window will be included; this means that if a safety

event is identified but diagnosis codes corresponding to the safety event are also observed during the clean window, it will not be counted to rule out pre-existing events.

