9.2.2. Exclusion Criteria

Individuals meeting any of the following criteria will be excluded from the study:

- Individuals with a record for atrial fibrillation or other supraventricular arrhythmia during the baseline period
- Individuals with missing date of birth

For the analyses using the SCRI design, a subset of eligible individuals from the ABRYSVO cohort that experienced atrial fibrillation or other supraventricular arrhythmia in the risk or control intervals will be included.

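### Table 1 lists a ventricular arrhythmia (I47.0) under the supraventricular outcome, so the code also enters the clean window and the exclusion from the primary AF cohort

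*Protocol*

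**What the plan says.** Protocol Section 9.3.2 makes the code list in Table 1 the definition ("The study outcomes and operational definitions of the outcome variables based on International Classification of Diseases, Tenth Revision, Clinical Modification (ICD-10-CM) diagnosis codes are outlined"): any listed code, whatever its position and whether from inpatient or outpatient care, identifies an event.

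- **Secondary outcome.** The row labelled "Supraventricular arrhythmia, including atrial fibrillation (secondary outcome" contains, under paroxysmal tachycardia, "I47.0, Re-entry ventricular arrhythmia". Under other cardiac arrhythmia it contains "I49.8, Other specified cardiac arrhythmias including Brugada syndrome, coronary sinus rhythm disorder, ectopic rhythm disorder, nodal rhythm disorder".
- **Primary outcome.** The AF row has four codes: I48.0, "I48.19, Other persistent atrial fibrillation", "I48.20, Chronic atrial fibrillation, unspecified" and I48.91. The secondary row takes in the same four by reference and adds three flutter codes.
- **Exclusion.** Section 9.2.2 removes "Individuals with a record for atrial fibrillation or other supraventricular arrhythmia during the baseline period". Section 9.3.2 applies the same two-year rule to incident cases of both outcomes and ties it to the codes of the safety event.
- **AF history.** Annex 3 Table A-2 defines AF before the baseline period by the same four AF codes.

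Section 9.3.3 promises that codes in the Annexes will be reviewed and updated in the SAP; that sentence does not mention Table 1. Section 9.7 allows the SAP to modify the plan but sends major changes to the primary endpoint definition to a protocol amendment.

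**The concern.** The outcome name and one of its codes contradict each other on the face of the table, and nothing in the protocol explains the inclusion. The list does two jobs, so the error appears in two places. It changes what the secondary outcome counts, and through the clean window it changes who is eligible for the primary AF analysis.

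In a safety study the direction matters. Counting events that the vaccine does not affect pulls a hazard ratio toward 1 and makes a real increase harder to see.

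There is a second, less certain worry about the AF list. Entries labelled as other or unspecified imply specified siblings, and none is listed. Specified persistent or chronic AF would then go unrecognised wherever the list is used.

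**Working it through.** No figure in the protocol depends on the code list, so there is none to reproduce. Table 2 rests on a background rate for AF alone, and I47.0 is not an AF code. The check is a reading of the definitions against each other, with one illustration.

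**1. I47.0 and the secondary outcome.** The label requires a supraventricular rhythm disorder, the code is described as ventricular, and any listed code suffices. A patient with I47.0 in the risk interval and a confirming diagnosis within 30 days is therefore counted as a supraventricular case.

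**2. I47.0 and the primary cohort.** The code is not among the four AF codes, so it cannot create a primary case. The exclusion in 9.2.2, however, covers AF and other supraventricular arrhythmia, and Table 1 is the only place where the latter is given codes. A person whose only relevant baseline record is I47.0 is removed from the AF cohort.

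**3. I49.8.** This is one code. Its description names Brugada syndrome but also coronary sinus, ectopic and nodal rhythm disorders. As listed it cannot be split, so it can only be kept, dropped or varied in a sensitivity analysis.

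**4. Effect on the secondary hazard ratio (illustration).** Let f be the share of comparator events that are not supraventricular. Assume that vaccination leaves them unchanged and that the true ratio is 2 for the rest. Then

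observed ratio = 2(1 − f) + 1·f = 2 − f.

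| f (assumed) | observed ratio |
|---|---|
| 1% | 1.99 |
| 5% | 1.95 |
| 10% | 1.90 |
| 20% | 1.80 |

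The share must be taken among comparator events, not among all counted events. None of these values of f comes from the documents.

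**5. The AF list.** Tracing a specified persistent or chronic AF code, if one exists outside the four, through each rule:

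- outcome: not identified;
- confirmation: does not count as the second diagnosis, so an initial I48.91 followed only by such a code is lost;
- clean window and 9.2.2: the person is not excluded;
- AF history: recorded as absent, both as a baseline covariate and as a candidate variable in the risk-factor model of Section 9.7.2.5.

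The errors run both ways: true cases can be missed and prevalent cases can be admitted.

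**The case against.** **The effect may be trivial.** The documents give no frequency for I47.0, and at f = 1% the ratio moves only from 2 to 1.99. The baseline exclusion applies alike to vaccinees and both control cohorts. This stands as a limit on size. It does not make a ventricular code supraventricular, and removal costs almost nothing.

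**The list cites a source, and I49.8 may be deliberate.** Both outcome rows cite a published study of rhythm abnormalities, which is not available here. A citation does not reconcile a label with a code that contradicts it. For I49.8 the point has force: including a mixed code may be a choice of sensitivity over specificity, so the request is for a justification or a with-and-without analysis. A reader might infer from the Brugada wording that the whole code is ventricular; its description does not support that.

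**The AF gap rests on the labels alone.** Which codes are missing cannot be settled from the protocol, hence the lower confidence. The word inclusive in the Table 1 header does not close the gap: reading I48.0 to I48.91 as a range would bring atrial flutter, listed separately, into the AF outcome.

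**A reader might go further and infer that prevalent AF leaking through the clean window materially inflates the primary incidence.** The documents do not support that. It would need the share of the cohort with only unlisted AF codes, their chance of a listed code in days 0-3 and their chance of confirmation, and none is given. High values for the second are hard to square with the design. These people have had no listed code for two years, about 182 four-day windows (730/4). If each window carried an independent 5% chance of one, the probability of none would be 0.95^182, about 0.01%. A visit on day 0 could raise coding, but so could earlier visits.

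**Chart review and the SAP may catch it.** Section 9.7.2.4 adjudicates up to 100 AF cases per report and may revise the algorithm if the lower limit of the PPV interval falls below 70% at the interim analysis. That could expose prevalent AF if adjudication tests new onset. It covers only AF cases in vaccinees, so it cannot show I47.0 or I49.8 events, wrongly excluded people or missed cases. The SAP, not seen here, may already have changed the list.

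**Conclusion.** The I47.0 point holds with high confidence: Table 1 contradicts the name of the outcome it defines, and the error carries into the exclusion for the primary cohort. Its consequences are non-supraventricular events in the secondary outcome and over-exclusion at baseline. It does not put false cases into the primary outcome. The dilution formula 2 − f rests on the added events being unaffected by vaccination; f is unknown and may be small.

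I49.8 is an unexplained mixed code, not a demonstrated error.

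The AF point holds with lower confidence. As labelled, the list leaves specified persistent and chronic forms out of the outcome, confirmatory, exclusion and history definitions. Neither the size nor the net direction of the effect on primary incidence can be stated from the documents.

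**What to change.** 1. Remove I47.0 from the secondary-outcome list and from the codes that define the clean window and the 9.2.2 exclusion.
2. For I49.8, either state why it is kept or report the secondary outcome with and without it.
3. Check the AF list against the ICD-10-CM tabular list. Complete the AF family at least in the exclusion list and the AF-history definition, and state whether any added codes also count as outcome or confirmatory diagnoses.
4. State in Section 9.2.2 which code list defines other supraventricular arrhythmia, so that exclusion and outcome cannot drift apart.

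The cost is an edit to Table 1, Annex 3 Table A-2 and Section 9.2.2, plus one extra run if I49.8 is varied. Under Section 9.7 a protocol amendment is needed if the primary endpoint definition changes materially. No new data are required.

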9.3.3. Baseline Characteristics

Data elements regarding baseline demographic and clinical characteristics will be assessed at index or based on a 2-year baseline period prior to the index date (ie, date of vaccination with ABRYSVO for ABRYSVO vaccinated individuals, date of vaccination with another vaccine for contemporary vaccinated controls, and assigned index date for contemporary unvaccinated controls). The demographic and clinical characteristics that will be assessed may include, but are not limited to, those that are listed below. The final list of baseline characteristics will be defined in the statistical analysis plan (SAP) based on feasibility and availability. All diagnoses, procedures, and medications will be identified by the ICD-10-CM diagnosis codes, International Classification of Diseases, Tenth Revision, Procedure Coding System (ICD-10-PCS) codes, CPT, or Healthcare Common Procedure Coding System [HCPCS] procedure codes, and generic drug names, as appropriate (Annex 3 Table A-2 and Annex 3 Table A-3; codes listed in the Annexes will be reviewed and updated in the SAP as necessary).

Demographics:

- Age
- Sex
- Race/ethnicity
- VHA service area (ie, US region)
- Marital status

ABRYSVO characteristics:

- Month and year of vaccination
- Care setting of vaccination

Clinical characteristics:

- Smoking status
- Body mass index (BMI)
- History of atrial fibrillation prior to baseline period (based on all available data rather than 2-year baseline)
- History of anaphylaxis/allergic reactions
- Previous anaphylaxis of vaccine component
- History of hospitalizations
- Frailty index
- Charlson Comorbidity Index (CCI)
- Alcohol abuse
- Alcohol dependence (excluding alcohol abuse)
- Prior infections within 90 days of the index date^{51,52}
- Selected comorbidities

- o Cardiovascular
 - Cardiomyopathy
 - Coronary artery disease (CAD)§
 - Cardiac valvular disease
 - CHF
 - Conduction disorder
 - Congenital heart disease§
 - Heart failure§
 - Hypertension
 - Myocarditis
 - Pericarditis
 - Stroke/Transient ischemic attack
- Hematological
 - Bleeding diathesis or condition associated with prolonged bleeding
 - Hematologic malignancy§
 - Sickle cell disease§
 - Thalassemia§
 - Venous thromboembolism (VTE)
- Hepatic
 - Hepatitis B virus (HBV)
 - Hepatitis C virus (HCV)
 - Liver disease§
- Immunological
 - Autoimmune disease
 - Immunocompromising conditions§
 - Islet transplant§
 - Solid organ transplant§
 - HSCT[§]
 - Hematologic or solid malignancy
 - HIV/Acquired immunodeficiency syndrome (AIDS)§
 - Moderate or severe primary immunodeficiency§
 - Rheumatologic/inflammatory conditions
 - Other immune deficiencies
- o Neurological/neuromuscular
 - Dementia (ie, Alzheimer's disease and related disorders, senile dementia)
 - Neurological disease
 - Neurologic or neuromuscular conditions causing impaired airway clearance or respiratory muscle weakness*§
 - Other neurologic diseases
- Respiratory
 - Asthma[§]
 - Chronic bronchiectasis
 - COPD/interstitial lung disease/emphysema§
 - Cystic fibrosis§

- Obstructive sleep apnea
- Pneumonia
- Other
 - Cancer
 - Chronic kidney disease/dialysis§
 - Diabetes mellitus without complications
 - Diabetes mellitus with complications§
 - Down syndrome
 - End-stage renal disease§
 - Gout
 - Hyperlipidemia
 - Hyperthyroidism (excluding autoimmune thyroiditis)
 - Illicit drug use (eg, cocaine)
 - Severe obesity (BMI ≥40 kg/m²)§
 - Stimulant use (eg, amphetamines, caffeine)
 - Metabolic syndrome
 - Panic disorders
 - Reaction to stress
- Concomitant medications[†]
 - Antineoplastic (ie, 7-con-o-methylnogaril, aclacinomycin a, cisplatin, doxorubicin, etaracizumab, ifosfamide, melphalan, mitoxantrone, trastuzumab)
 - o Bisphosphonates (ie, alendronate)
 - o Cardiovascular (ie, adenosine, dobutamine)
 - o Central nervous system (ie, clozapine, morphine)
- Other medications/procedures (identified outside of the American Heart Association [AHA] criteria)
 - o Nonsteroidal anti-inflammatory drugs (NSAID)
 - o Ivabradine
 - o Respiratory (ie, theophylline)
 - o Digitalis
 - CAR T-cell therapy*§
- History of immunizations
 - Seasonal influenza vaccine
 - o COVID-19
 - Tetanus diphtheria and pertussis (tetanus diphtheria and acellular pertussis vaccine [Tdap] or tetanus diphtheria and pertussis vaccine [Td])
 - o Chickenpox (varicella)
 - o Shingles (herpes zoster recombinant and/or live)
 - Human papillomavirus (HPV)
 - o Pneumococcal conjugate
 - Pneumococcal polysaccharide
 - o Hepatitis A
 - o Hepatitis B

- Meningococcal conjugate vaccine (MenACWY) and serogroup B meningococcal vaccine (MenB)
- Haemophilus influenzae type b
- Co-administered immunization (same list as history of immunizations)
- Residing in a nursing home*§
- * ICD-10-CM diagnosis codes, ICD-10-PCS codes, CPT, HCPCS procedure codes, or operational definition based on other data available in VHA's CDW will be provided in the SAP.
- † The list of concomitant medications was derived from the AHA's scientific statement regarding drug-induced arrhythmia, which is based on a literature search.⁵³ Since the level of evidence varies substantially across articles and reports identified by the AHA, only drugs with relative risk (ie, incidence rate ratio [IRR], hazard ratio, or odds ratio) or 95% CI upper limit greater than 3 or incidence/proportion of patients experiencing atrial fibrillation greater than 10% were included to ensure a higher degree of certainty that the drug is actually associated with atrial fibrillation. Drugs with evidence based on case reports only were not included. Note that alcohol was not included despite meeting the criteria as it is included as a clinical characteristic.
- § Conditions that increase the risk of RSV as defined according to CDC. 19

9.4. Data Sources

The VHA is the largest integrated health care system in the US, providing both IP and OP clinical care to over 9 million Veterans enrolled at more than 170 medical centers and 1,113 community-based OP clinics. ²⁰ VHA's health care delivery system is organized regionally around 18 Veterans Integrated Service Networks (VISNs) across the US. Each VISN is responsible for health care planning and resource allocation in a particular geographical region. For example, VA New England Healthcare System (VISN 1) covers VHA facilities in Massachusetts, Connecticut, New Hampshire, Maine, and Rhode Island, while VA Heart of Texas Health Care Network (VISN 17) oversees the facilities in Texas. The VHA also maintains its own mortality data where 99% of enrollees' deaths are reported within one month of occurrence.

The objectives of this study will be addressed using data from VHA's CDW, which is an integrated EHR system with a centralized data warehouse that is updated on a daily basis. The CDW stores data in separate databases, one for each type of clinical information (eg, IP medication, IP admission, OP medication, OP visit). Individual demographic information such as date of birth and gender are also available. Immunization records include information on manufacturer, lot number, injection site, and history of immunizations. The CDW lacks information on care received outside of a VHA facility.

Each individual is assigned a unique identification number to allow for longitudinal follow-up as well as to cross-reference to the various separate databases. For example, in each IP admission record, there is information on the primary discharge diagnosis (and as many as 15 secondary diagnoses), date of admission, date of discharge, and length of stay. This record can then be linked to other information of that IP stay located in other files,

including procedures that the patient underwent during the hospitalization, medical specialty of the provider, and prescriptions dispensed. Other files are similarly structured, and therefore may be linked together to provide comprehensive information about the patient and his/her medical encounters.

The VHA database is an appropriate data source to evaluate the safety of the ABRYSVO vaccine for the following reasons. First, VHA data are refreshed daily and would thus enable early data analysis. Second, the VHA population is on average older than the general US population.⁵⁴ Of these, about 30% (roughly 1,000,000 individuals) use VHA health services almost exclusively (ie, those with a priority group of 1 or 4; Veterans assigned to priority group 4 are either accepting VA assistance or housebound benefits, or have been determined to be "catastrophically disabled" by the VA.⁵⁵), which lends itself to having complete, longitudinal healthcare data for such individuals who may be at higher risk of RSV.^{56,57} These priority groups include Veterans with the highest levels of service-connected disability and are therefore, the highest priority for VHA care.⁵⁵ Finally, the VHA population has, on average, more comorbid conditions than the general population, which also indicates that these individuals may be at higher risk of RSV.⁵⁸ While the VHA population is predominantly male (approximately 90%), and thus lacks generalizability to females, it will still provide a useful setting to examine real-world vaccine safety.

Since it is possible that individuals may not have all their health encounters within the VHA, (especially older veterans who are also covered by Medicare), the CDW data will be supplemented with data from CMS as a subgroup analysis, linking Medicare administrative claims data at the patient level to ensure a more comprehensive evaluation of the care an individual receives. Medicare data will include eligibility files and claims for Fee-For-Service (FFS) billable healthcare services received in the IP and OP setting, as well as skilled nursing facility (SNF), hospice, and home health agencies, and will cover the US primarily among those 65 years of age and older. Medicare FFS claims data are comprised of six different types of data files, with a unique identifier for each beneficiary, allowing linkage across all data files. Below is a summary of the different datasets:

Master Beneficiary Summary File (MBSF): This dataset contains information on beneficiary enrollment for each calendar month in Medicare Parts A, B, and D. Eligibility for sample selection, including original and current enrollment reason, and baseline characteristics, specifically demographic information, will be obtained from these data files.

Inpatient Claim File: FFS claims submitted by providers for cost reimbursement for services received during hospitalizations and ED visits are included in this dataset. Up to 25 diagnosis fields, including the admission diagnosis as well as a principal diagnosis, are available on each claim.

Outpatient Claim File: FFS claims that institutional, OP providers submit for reimbursement are available in this dataset. These include OP departments, rural health clinics, renal dialysis facilities, OP rehabilitation facilities, comprehensive OP rehabilitation facilities, Federally Qualified Health Centers, and community mental health centers. Up to 25 diagnosis fields as well as CPT codes are available for each OP claim.

Carrier File: Carrier datasets contain FFS claims submitted by professional providers, including physicians, physician assistants, clinical social workers, and nurse practitioners. Claims from freestanding facilities (eg, independent clinical laboratories) are also present in the Carrier files. These files contain up to 12 diagnosis fields as well as CPT codes.

SNF Claim File: This dataset contains FFS claims for paid services that are submitted by SNF institutional facility providers. Up to 25 diagnosis fields, including the admission diagnosis as well as a principal diagnosis, are available on each claim.

Prescription Drug Event (PDE) File: All medications dispensed at OP pharmacies that are submitted for reimbursement are available in this dataset. The NDC variable will be used in this study to identify all medications dispensed, and will also include some vaccinations, including ABRYSVO.

